### 1.1 Background

Men with erectile dysfunction (ED) refractory to conservative therapies are often recommended to undergo placement of an inflatable penile prosthesis (IPP). However, one of the most common complaints after surgery is that the men feel that their penis is shorter than what it was previously. This is likely due to one of several factors including the underlying disease process which resulted in loss of penile length, effects of aging on penile length (loss of elasticity; increased fibrosis), changes in abdominal physiology (development of pre-pubic fat pad that obscures the penis), and recall bias (incorrect assumptions on prior penile length).

Several attempts have been made by investigators to optimize penile length prior to placement of the penile prosthesis, including adjunctive surgical maneuvers (excision of suprapubic fat pad, release of suspensory ligament, direct penile extension), use of injectable materials, and pre-operative use of penile traction therapy (PTT). In a small pilot study of 10 men undergoing IPP, Levine and colleagues recommended the use of the Andropenis PTT  $\geq 2$  hours daily for 2-4 months. At 15 months follow-up, patients achieved a +1.6 cm increase compared to pre-traction stretched length, and +0.9 cm increase following penile prosthesis (PP). Results from a non-validated satisfaction questionnaire demonstrated that no patients reported loss of length following surgery. Unfortunately, the study did not include a control group, thus limiting the conclusions which may be drawn.

Compared to other options, PTT offers several potential advantages in that it is minimally-invasive, does not increase the morbidity of surgery, and has not been shown to result in any long-term side effects.

Recently, Mayo Clinic licensed a new PTT concept to PathRight Medical, who subsequently developed the RestroreX PTT device. This is classified as a Class I device, not requiring clinical human trials. The purported benefits with the RestroreX device over other PTT systems include ability to generate constant traction, user-feedback on appropriate use, improved comfort, and ability to track improvements. The device is currently utilized in 30-minute intervals, with up to 3 sessions performed per day.

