Given the clinical issue of dissatisfaction with penile length post IPP, the potential role for PTT, and limited amount of data available, we sought to perform a clinical trial evaluating the effect of PTT on increasing the total length of prosthesis which can be inserted. We additionally sought to determine if PTT resulted in improved post-operative satisfaction on total penile length achieved.

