# **2 Study Objectives**

## **2.1 Primary Objective**

1. The primary objective is to assess the length of the penile prosthesis inserted into subjects following completion of RestoreX® traction therapy compared to control groups (no treatment).

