### **3.5 Study Schema**

During the initial scheduled clinic appointment, the patient will receive a description of the study, and informed consent. Potential subjects will be notified about the two groups for the study: Treatment (PTT for 30 min 3x/day for 3 months) or No Treatment (control). Subjects planning to have their IPP procedure immediately and do not want to utilize traction therapy will be considered for the control group. Subjects who wish to wait for placement of IPP and are interested in utilizing traction will enter into the treatment group. Those consenting will receive initial study assessments and subjects who take part in the treatment group will be educated on how to use the device properly.

Patients will then be given a baseline questionnaire to complete and, if assigned to the treatment group, begin using the device. Patients in the treatment arm will record a daily journal of their usage of the device.

After 3 months (+1.5 months permitted), patients in the treatment arm will return for their scheduled procedure (control arm patients will undergo surgery without a 3-month delay). Only those who utilized the device for 3 months will be asked to complete a follow-up questionnaire at this time. Patients will also be encouraged to self-report any additional adverse events (AE's) that they encountered over the 3 months of using the therapy.

During surgery, data will be recorded by the surgeon to indicate type, length and approach taken for penile prosthesis implanted as well as any complications of penile prosthesis implantation. These complications may include urethral perforation, corporal perforation, device malfunction, bowel injury or vascular injury; all of which are standard potential complications of the surgery.

Following surgery, patients will be seen in the clinic based on the standard routine clinical practice. During these follow-up appointments, penile length measurements will be performed and recorded.

Patients will also be sent questionnaires by email or by mail (if email not available) at 3, 6, and 12 months post-operatively. If a patient has not returned their questionnaire within 2 weeks, a follow up phone call to the patient will be placed as a reminder. Alternatively, patients may answer the questions over the phone if that method is preferable.

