**Table 2: Schedule of Events for Control Group**

Study Activity	Baseline	3 Month	6 Month	12 Month
Consent	X			
Baseline Questionnaire	X			
Length Assessment	X			
Penile Prosthesis Implanted	X			
Penile Prosthesis Length Recorded	X			
PP Follow-Up Questionnaire		X	X	X
Chart Review of Post-Op Complications				X

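### Section 3.5 ties traction to waiting and no traction to immediate surgery, so the trial compares traction plus deferral with prompt surgery rather than traction with no traction

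*Combined protocol and SAP*

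**What the plan says.** The entry rule in section 3.5 has two sentences. For controls: "Subjects planning to have their IPP procedure immediately and do not want to utilize traction therapy will be considered for the control group". For treatment: "Subjects who wish to wait for placement of IPP and are interested in utilizing traction will enter into the treatment group". Timing and traction are joined in both. A man who declines traction but whose operation is booked for later, for ordinary reasons, is described by neither.

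The same section fixes the timing of surgery. "After 3 months (+1.5 months permitted), patients in the treatment arm will return for their scheduled procedure", while "control arm patients will undergo surgery without a 3-month delay". The schedules in section 4.6 agree: the row "Penile Prosthesis Implanted" is marked under 3 Month in Table 1 (treatment) and under Baseline in Table 2 (control).

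The question is framed without timing. Section 1.1 describes a trial "evaluating the effect of PTT on increasing the total length of prosthesis which can be inserted". Section 2.1 compares implant length after traction with no treatment, and the Study Summary defines the reference group as men using no traction. Section 5.2 normalizes to pre-operative stretched length, and the Study Summary stratifies by baseline length. Neither mentions the interval from baseline to surgery.

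**The concern.** If every treated man is operated on 3 to 4.5 months after baseline and every control soon after it, arm and waiting time are nearly the same variable. Whatever changes during the wait is counted as part of the traction effect, adding to it or subtracting from it. This would be so even if the men in the two arms were identical, so it is a different problem from self-selection, and adjusting for patient characteristics does not touch it.

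At stake is the wording of the main conclusion. Section 2.1 invites a statement about traction, but the design supports a statement about a strategy: wait and use traction, or go straight to surgery. A repeat length measurement just before surgery would not help, because no control has a matching interval against which to read it.

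**Working it through.** **Inputs.** Treated interval 3 to 4.5 months (section 3.5). Control interval: no maximum is stated; section 3.5 excludes a 3-month delay and Table 2 shows Baseline. Completers: at least 20 per arm (section 3.4, from 40 accrued per arm and 80 in all, so 20/40 = 50% completion is expected). The plan gives no power calculation, SD or rate of change with time, so it has no figure of its own to reproduce here. Assumption: waits are uniform over each stated range.

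**Step 1: deferral as yes/no.** Take a model with an intercept, traction, deferred (yes/no) and baseline length. With the two groups of section 3.5, the traction and deferral columns are identical. The matrix has rank 3 for 4 columns, so the two effects cannot be estimated separately at any sample size.

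**Step 2: interval in months, with a linear effect.** For a uniform range of width w the variance is w²/12. Treated: mean 3.75, variance 1.5²/12 = 0.1875. With equal arms:

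- within-arm variance W = (0.1875 + control variance)/2
- between-arm variance B = ((3.75 − control mean)/2)²
- squared arm–interval correlation r² = B/(B + W)
- variance inflation VIF = 1/(1 − r²) = (B + W)/W
- SE of the arm effect, in residual SDs, = √(2/20) × √VIF = 0.316 × √VIF

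| Control wait (months) | Mean, variance | W | B | r | VIF | SE (SD) |
|---|---|---|---|---|---|---|
| all at 0 | 0, 0 | 0.0938 | 3.516 | 0.987 | 38.5 | 1.96 |
| 0 to 1 | 0.5, 0.0833 | 0.1354 | 2.641 | 0.975 | 20.5 | 1.43 |
| 0 to 3 | 1.5, 0.75 | 0.4688 | 1.266 | 0.854 | 3.7 | 0.61 |
| 0 to 4.5 | 2.25, 1.6875 | 0.9375 | 0.5625 | 0.612 | 1.6 | 0.40 |

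The unadjusted SE is 0.316 SD. Simulating the first row with 20 per arm gave a VIF of about 41 and an SE of about 2.0 SD, in line with the formula.

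**Step 3: overlap.** In the first three rows the two ranges at most touch at 3 months, so separating traction from interval rests wholly on the linear assumption. In the last row 1.5/4.5, or one third, of controls fall in the treated range: about 7 of 20.

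**Step 4: precision of the interval slope.** In the last row its SE is 1/√(40 × 0.9375) = 0.163 SD per month.

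**The case against.** Five arguments can be made for leaving section 3.5 alone.

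*The wait is part of the regimen.* Section 1.2 defines treatment as use for 3 months before implantation, so traction-then-surgery against surgery is a legitimate comparison. That is true, but sections 1.1 and 2.1 do not present it that way, and no passage redefines the control as prompt surgery. The argument supports changing the conclusion's wording, not leaving it.

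*Time may be nearly neutral, or may work against traction.* Section 1.1 cites the "underlying disease process which resulted in loss of penile length, effects of aging on penile length" to explain why men feel shorter than before. That describes long-run loss and gives no rate over months. Such loss would make a positive result conservative. This stands. A reader might infer that waiting could produce a falsely positive traction result, or might assume a monthly drift and express it as a share of the earlier pilot's gain. The documents support neither: they name no mechanism that lengthens the implant during a wait, give no drift rate, and say that the pilot did not use length of device inserted (section 1.3).

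*Immediate is undefined.* Controls may in practice wait some weeks. This also stands. A reader might infer that no adjustment can ever separate arm from interval. That holds for practical purposes only if controls wait about a month or less. At 0 to 3 months the variance inflation is 3.7, although it then relies on linearity.

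*The remedy is weak.* A slope SE of 0.16 SD per month cannot detect a small drift, the uniform 0 to 4.5 month spread is hopeful, and later-operated controls would have their own reasons for delay. All true. But the target is the arm effect, whose SE rises only from 0.32 to about 0.40 SD in that best case, so the model is worth running if such men enrol.

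*Self-selection is probably the larger problem.* Agreed. It arises from the same rule, and this change does not cure it.

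**Conclusion.** The concern holds as a mismatch between the question and the group definition. Followed as written, section 3.5 makes arm and baseline-to-surgery interval nearly coincide, and the trial estimates traction with a 3 to 4.5 month deferral against prompt surgery without traction. Nothing in section 5.2 or the Study Summary separates the two.

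The bias itself cannot be sized: neither the magnitude nor the direction of a wait effect is documented. What can be sized is how far adjustment could help, and that depends on when controls are actually operated on, from little or no use at 0 to 1 month to a modest loss of precision at 0 to 4.5 months. Those figures assume uniform waits, a linear interval effect and 20 completers per arm. The change is worth making because it is cheap, not because the documents show a large bias.

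**What to change.** 1. In section 3.5, drop 'immediately' as a condition of control entry. Any eligible man who does not want traction may be a control, whatever the date of his already planned operation. The study delays nobody's surgery.
2. Align the phrase about controls having no 3-month delay, and Table 2. Time control follow-up from surgery, as the questionnaire text in section 3.5 already does.
3. Report the baseline-to-surgery interval by arm, from the baseline and surgery dates.
4. In section 5.2, add one sensitivity model for implant length that includes arm, interval and baseline length. State that it is informative only if enough later-operated controls enrol, that it assumes a linear interval effect, and that it does not remove self-selection.
5. If few such controls enrol, word the conclusion as 'traction with a 3 to 4.5 month deferral versus prompt surgery without traction'.

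The cost is a few edits to section 3.5, Table 2 and section 5.2, plus one model. It needs no extra patients, and the pool of possible controls grows. The downside is more variable control timing and a wider standard error in the sensitivity model: at best about 0.40 against 0.32 SD with 20 per arm.

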## 2.2 Secondary Objective

1. Compare patient compliance with traction device.
2. Compare patient reported satisfaction with use of traction device.
3. Evaluate any adverse events (AEs) with use of RestoreX® for penile lengthening.
4. Compare intra- and/or post-operative complication rates.
5. Compare pre- and post-operative stretched penile lengths.
6. Compare patient satisfaction scores including satisfaction with overall penile length.

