### **3.4 Consent and Accrual**

During the patient's consultation appointment, they will receive a description of the study and if the patient expresses interest in participating, a formal consent will be reviewed (see **Attachment – Consent Form**).

If the patient successfully completes the consenting process, they will undergo initial study penile length assessments (described later in the protocol). Those wishing additional time to consider participation may be rescheduled to a later date if desired.

At the time of consent, all participants will be assigned a study identifier, with a master list maintained in a password protected database (Mayo server) linking the patient to the identifier. A total of 40 patients will be accrued into each arm of the study, for a total of 80 patients accrued overall. It is estimated that 80 patients will need to be accrued in order to achieve a minimum of 20 subjects in each arm that will complete the study from start to finish.

No limitations will be applied to either clinical site for enrollments, such that it is possible that one clinical site may enroll 100% of the patients.

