### 4.2 Follow-up Visit – Treatment Group

- Questionnaire after penile traction, but before IPP surgery

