#### **4.6 Schedule of Events**

**Table 1: Schedule of Events for Treatment Group**

Study Activity	Baseline	3 Month	6 Month (3 months post-op)	9 Month (6 months post-op)	15 Month (12 months post-op)
Consent	X				
Baseline Questionnaire	X				
Length Assessment	X				
Patient Diary Provided	X				
PTT Experience Questionnaire		X			

Penile Prosthesis Implanted		X			
Penile Prosthesis Length Recorded		X			
PP Follow-Up Questionnaire			X	X	X
Chart Review of Post-Op Complications					X

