## **6.5 Recording of Adverse Events**

The study team will seek information on adverse events by specific questioning between baseline and the 3 month visit. Information on all adverse events will be recorded immediately in the adverse event section of the specific questionnaire as well as in an adverse event form (see Attachment – Adverse Event Form).

All adverse events occurring during the study period will be recorded. The clinical course will be followed until resolution, stabilization, or until it has been ultimately determined that the study treatment or participation is not the probable cause. Serious adverse events that are still ongoing at the end of the study period will be followed up, to determine the final

outcome. Any serious adverse event that occurs after the study period and is considered to be at least possibly related to the study treatment or study participation will be recorded and reported immediately.

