### **6.6.2 Stopping Rules**

Any serious adverse event which is determined to reasonably be related to the study device by the sponsor-investigator will result in immediate discontinuation of the therapy. If 5 patients develop serious adverse events, the study will be halted with re-review required by the Mayo IRB prior to consideration of study resumption.

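### Section 3.5 can be read as withholding the traction questionnaire from men who stop the device early, so reported device satisfaction would probably be too favourable

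*Combined protocol and SAP*

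**What the plan says.** Three places in the protocol deal with a questionnaire on the traction experience.

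- Section 3.5, describing the return for surgery after 3 months: "Only those who utilized the device for 3 months will be asked to complete a follow-up questionnaire at this time". The sentence before it, in a parenthesis, says that "control arm patients will undergo surgery without a 3-month delay".
- Section 4.2, headed for the treatment group, has one entry: "Questionnaire after penile traction, but before IPP surgery". It carries no condition on completing traction.
- Table 1 lists a "PTT Experience Questionnaire" in the 3 Month column for the treatment group, also without a condition.

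The names differ, but the timing and purpose match, so I take them to be one instrument.

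Secondary objective 2 in section 2.2 is: "Compare patient reported satisfaction with use of traction device". Section 5.2 says that questionnaire responses will be compared, but names no denominator and does not say how men who stop early are handled. No questionnaire or visit at discontinuation is described anywhere. The surveys at 3, 6 and 12 months after surgery (section 4.4) go to both groups; the text does not show that they ask about the traction device.

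**The concern.** Discomfort, dissatisfaction and adverse effects are plausible reasons for giving up a device meant to be worn three times a day for 3 months. If the questionnaire reaches only men who lasted the 3 months, inclusion depends on something close to the outcome itself. The result would describe satisfaction among men who tolerated the device, yet could be presented as satisfaction among men who were given it. The same applies to any tolerability items on the form.

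The plan as written would not reveal the size of the problem. It neither asks the stoppers nor requires a count of how many men started, stopped and answered. Opinions not sought when traction stops are hard to recover later.

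**Working it through.** **Step 1: the two readings of section 3.5.**

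| Man in the treatment arm | Literal reading (3 months of use required) | Milder reading (treatment arm, not controls) |
|---|---|---|
| Uses the device for 3 months, returns for surgery | asked | asked |
| Stops early, returns at 3 months | not asked | asked |
| Stops early, does not return at 3 months | not asked | not asked |

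Section 4.2 and Table 1 fit the milder reading. The bottom row is a gap under both, because the only scheduled occasion is the 3-month visit.

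**Step 2: the plan's own figure.** Section 3.4 accrues 40 per arm: "It is estimated that 80 patients will need to be accrued in order to achieve a minimum of 20 subjects in each arm" completing the whole study. This is consistent with 50% non-completion: 20 / (1 − 0.50) = 40 per arm, and 2 × 40 = 80. The 50% is inferred from 40 and 20; it is not stated. It covers the whole study, including follow-up to 12 months after surgery, and applies equally to controls, who use no device. It is therefore not a traction stop rate, and the documents give none.

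**Step 3: size of the effect under stated assumptions.** From the plan: 40 men in the treatment arm. Assumed: 10%, 25% or 50% are not asked because they stopped; about 80% of completers are satisfied; 20% or 50% of stoppers are satisfied. All completers are taken to respond.

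Let *k* be the number of satisfied completers, *c* the completers, *s* = 40 − *c* the stoppers, and *p* the satisfaction rate in stoppers.

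- Reported rate = *k* / *c*
- Rate in all users = (*k* + *p* × *s*) / 40
- Overstatement = the difference, which equals (*s* / 40) × (*k* / *c* − *p*)

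| Stop | *c*, *s* | Reported | All 40, *p* = 20% | All 40, *p* = 50% | Overstatement (points) | Bounds for all 40 |
|---|---|---|---|---|---|---|
| 10% | 36, 4 | 29/36 = 80.6% | 29.8/40 = 74.5% | 31/40 = 77.5% | 6.1 or 3.1 | 29/40 = 72.5% to 33/40 = 82.5% |
| 25% | 30, 10 | 24/30 = 80% | 26/40 = 65% | 29/40 = 72.5% | 15 or 7.5 | 24/40 = 60% to 34/40 = 85% |
| 50% | 20, 20 | 16/20 = 80% | 20/40 = 50% | 26/40 = 65% | 30 or 15 | 16/40 = 40% to 36/40 = 90% |

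The bounds take every stopper as dissatisfied, then every stopper as satisfied. If *p* equals the completers' rate, the overstatement is zero. The upper bounds exceed the reported rate, so the sign is not fixed by arithmetic; it rests on stoppers being less satisfied. Under the milder reading, *s* counts only stoppers who do not return, so the effect is smaller.

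**Step 4: adverse events.** Section 6.5 says: "Information on all adverse events will be recorded immediately in the adverse event section of the specific questionnaire". The same sentence goes on to require a separate adverse event form. The section also commits the team to specific questioning between baseline and the 3-month visit and to recording all events in the study period. None of this is limited to completers. What remains is narrower: Table 1 schedules no contact between baseline and 3 months, so that questioning has no fixed occasion in a man who stops and stays away.

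**The case against.** The best case for the plan is that section 3.5 is loosely worded. The preceding contrast with controls suggests that the sentence means only that controls skip this form, and section 4.2 and Table 1 agree. A man who stops at week 3 and comes back for surgery would then be asked. This is a fair reading, and it means the exclusion of all early stoppers is not established. It does not close the gap for men who stop and do not return, and three places that can be read differently still need reconciling.

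The questionnaires are also attachments outside the text, so their content cannot be checked. A post-operative survey might ask about traction. That stands as a limit on the point: the text does not show another source for device satisfaction, which is different from showing that there is none.

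A reader might infer three stronger things that the documents do not support.

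- That this questionnaire is the main source for device adverse events. Section 6.5 provides questioning and a separate form. A man with a device-related serious event, which under section 6.6.2 "will result in immediate discontinuation of the therapy", is not lost from the safety data, because section 6.6.1 requires a form for every serious event. Under the literal reading only his opinion of the device is lost.
- That half the treatment arm will stop traction. The figures in section 3.4 do not measure that (step 2).
- That compliance rests on this questionnaire. Its stated source is the daily diary, which section 3.5 does not confine to completers, although no return of the diary is scheduled.

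**Conclusion.** The point holds for device satisfaction and for any tolerability items on the same form. Sections 3.5 and 4.2 and Table 1 must be reconciled, and under either reading some men who give up the device early are never asked about it. Reported satisfaction would probably be too favourable, by about 3 to 30 percentage points under the assumed rates in step 3, and by nothing if stoppers are as satisfied as completers. Those rates are assumptions, so it would be too strong to say that the result is certain to look better than the truth. Adverse events are less affected, with a residual weakness in when stoppers are questioned. Severity is moderate: one secondary objective is at risk, and the primary comparison of prosthesis length is untouched.

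**What to change.** Replace the sentence in section 3.5 with wording such as: *Every treatment-arm subject who used the device at least once will be asked to complete the traction questionnaire and return the diary when traction stops or before surgery, whichever is first, by REDCap, mail or telephone.* Make section 4.2 and Table 1 match, and use one name for the questionnaire throughout.

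Add to section 5.2 that device satisfaction is reported for all men who used the device, with the number responding, and separately for stoppers and completers. The same contact would give the questioning in section 6.5 a definite occasion in men who stop.

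The cost is some protocol wording, one survey trigger and a few extra contacts through channels that section 4.4 already uses. The satisfaction figures may come out less favourable. Some stoppers will not answer, which is why the number responding must be shown.
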